3.5.5 Discontinuation of study treatment components

The reasons for discontinuation of ribociclib/placebo will be summarized by treatment arm for the double-blind on-treatment period, based on the information on the ribociclib/placebo DAR CRF for patients who have the “dose permanently discontinued” box checked.

Partial discontinuation: A partial discontinuation is defined as the event when the last non-zero dose of ribociclib/placebo is more than 21 days before the last non-zero dose of fulvestrant when the permanent discontinuation checkbox is checked in the ribociclib/placebo DAR page. Partial discontinuation of ribociclib/placebo will be summarized by treatment for the double-blind on-treatment period.

The reasons for discontinuation and partial discontinuation will be listed using the cross-over analysis set separately.

3.6 Concomitant and post-treatment therapy

Concomitant therapies

Concomitant therapy is defined as all interventions (therapeutic treatments and procedures) besides the study treatment that were administered to a patient, coinciding with the study assessment period (even if started before the study assessment period).

Concomitant medications will be coded using the World Health Organization (WHO) Drug Reference Listing (DRL) dictionary that employs the WHO Anatomical Therapeutic Chemical (ATC) classification system.

Concomitant medications will be summarized by lowest ATC class, preferred term and treatment arm. The summary will include medications starting on or after the start of study treatment but no later than 30 days after last dose of study treatment or before the start of open-label ribociclib plus fulvestrant treatment.

The safety set will be used for all concomitant medication tables and listings.

Concomitant medications will be listed also for the cross-over period using the cross-over analysis set. Any concomitant therapies starting more than 30 days after the last date of cross-over open-label study treatment will be flagged in the listing.

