### **10.3 Treatments (study treatment, concomitant therapies, compliance)**

The safety set will be used for the analyses below.

The actual dose and duration of fulvestrant, and ribociclib/placebo treatment, as well as dose intensity (computed as the ratio of actual dose received to actual duration) and the relative dose intensity (computed as the ratio of the dose intensity to planned dose received/planned duration), will be listed and summarized using descriptive statistics. The total daily doses of fulvestrant and ribociclib/placebo for each patient will be summarized using descriptive statistics (e.g. mean, median, and mode).

[figure not shown]
Concomitant medications and significant non-drug therapies will be listed by patient and summarized by ATC (Anatomical Therapeutic Chemical classification system) term for each treatment group. These summaries will include medications starting on or after the start of study treatment or medications starting prior to the start of study treatment and continuing after the start of study treatment. Any prior concomitant medications or significant non-drug therapies starting and ending prior to the start of study treatment will be listed.

Compliance to the study drug will be assessed by the number of dose reductions and dose interruptions.

The duration of exposure to study treatment and each component of study treatment will also be summarized for the cross-over phase in patients who crossed over to LEE011 combination therapy after unblinding (i.e. using the Cross-over analysis set).

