Appendix 1	CTC grades for laboratory values in Novartis Oncology.....	28

List of tables

Document History – Changes compared to previous version of SAP.....	2
Table 1-1 Study objectives	10
Table 2-1 Last contact date data sources	13
Table 2-1 Patient classification based on protocol deviations and non- protocol deviation criteria	15
Table 3-1 Planned dose intensity.....	19
Table 3-2 Clinically notable ECG values.....	25

List of figures

Figure 1-1 Study Design	9
-------------------------------	---

List of abbreviations

AE	Adverse event
AESI	Adverse events of special interest
ATC	Anatomical Therapeutic Chemical
BOR	Best overall response
CI	Confidence Interval
CBR	Clinical benefit rate
CR	Complete response
CRF	Case Report Form
CRS	Case retrieval sheet
CSR	Clinical study report
CT	Computed tomography
CTCAE	Common Terminology Criteria for Adverse Events
DAR	Dosage administration Record
DI	Dose Intensity
DOR	Duration of Response
ECG	Electrocardiogram
ECOG	Eastern Cooperative Oncology Group
EORTC QLQ-C30	European Organization for Research and Treatment of Cancer Core 30-item Quality of Life Questionnaire
EOT	End of treatment
ER	Estrogen receptor
FAS	Full analysis set
HER2	Human epidermal growth factor receptor 2
HR	Hazard Ratio
HR	Hormone receptor
MBC	Metastatic breast cancer
MedDRA	Medical Dictionary for Regulatory Activities
NCI	National Cancer Institute
NMQ	Novartis MedDRA queries
ORR	Overall response rate
OS	Overall survival
PD	Progressive disease
PDI	Planned dose intensity
PDS	Programming Datasets Specifications
PFS	Progression-free survival
PR	Partial response
PS	Performance Status
PT	Preferred term
QTcF	QT interval corrected by Fridericia method
RDI	Relative dose intensity
RECIST	Response Evaluation Criteria In Solid Tumors

SAE	Serious adverse event
SAP	Statistical Analysis Plan
SD	Stable disease
SD	Standard deviation
SMQ	Standardized MedDRA queries
SOC	System organ class
TFL	Tables Figures and Listings
TBIL	Total Bilirubin

1 Introduction

This document describes the detailed statistical methodology to be used for the final Clinical Study Report (CSR) of study CLEE011F2301, a phase III, randomized, double-blind, placebo-controlled study of ribociclib or placebo in combination with fulvestrant for the treatment of men and postmenopausal women with hormone receptor positive, HER2-negative, advanced breast cancer who have received no or only one line of prior endocrine treatment.

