The content of this SAP is based on CLEE011F2301 protocol amendment 4 (Jan 29, 2020). All decisions regarding final analysis, as defined in the SAP document, have been made prior to database lock and unblinding of the study data.

CSR deliverables (shells for tables, figures, listings) and further programming specifications are described in Tables Figures and Listings (TFL) shells and Programming Datasets Specifications (PDS) documents, respectively.

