3.7 Concomitant and post-treatment therapy

Concomitant therapies

Concomitant therapy is defined as all interventions (therapeutic treatments and procedures) besides the study treatment that were administered to a patient, coinciding with the study assessment period (even if started before the study assessment period).

Concomitant medications will be coded using the World Health Organization (WHO) Drug Reference Listing (DRL) dictionary that employs the WHO Anatomical Therapeutic Chemical (ATC) classification system.

Concomitant medications will be summarized by lowest ATC class, preferred term and treatment arm. These summaries will include:

1. medications starting on or after the start of study treatment but no later than 30 days after last dose of study treatment, and
2. medications starting prior to the start of study treatment and continuing after the start of study treatment.

All concomitant therapies will be listed. Any concomitant therapies starting and ending prior to the start of study treatment or starting more than 30 days after the last date of study treatment will be flagged in the listing.

[figure not shown]
The safety set will be used for all concomitant medication tables and listings.

Concomitant medications that have the potential to impact some specific analyses (e.g. PK, efficacy or safety analyses) will be identified prior to database lock. Separate summaries of these concomitant medications will be produced using the appropriate analysis set (e.g. FAS for those potentially affecting efficacy).

- Strong inhibitors or inducers of CYP3A4/5, substrates of CYP3A with a narrow therapeutic window, medications with a known risk of QT prolongation and other prohibited medications described in [Section 2.4](#) will be identified. They will be tabulated by ATC class and preferred term.
- Any anti-neoplastic therapy administered concomitantly with study treatment will be listed based on their identification through the protocol deviation process.

Post treatment anti-neoplastic therapy

Anti-neoplastic therapies after discontinuation of study drug will be listed and tabulated by ATC class, preferred term and treatment arm by means of frequency counts and percentages using the FAS. In addition, 1st line and 2nd line anti-neoplastic medications after discontinuation of study drug will be summarized by medication type, e.g. hormonal therapy, chemotherapy, etc. The medication type will be determined by clinical review.

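### The final-CSR SAP's concomitant-medication table rule leaves out drugs begun before first dose and continued, against its own definition and Protocol 10.3

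*SAP*

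**What the plan says.** The SAP file holds two plans. The later one governs the final report ("This document describes the detailed statistical methodology to be used for the final Clinical Study Report (CSR") and rests on the current protocol: "The content of this SAP is based on CLEE011F2301 protocol amendment 4 (Jan 29, 2020").

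Its Section 3.6 first defines concomitant therapy as any intervention, other than study treatment, that overlaps the study assessment period, "even if started before the study assessment period". It then gives the table rule: "The summary will include medications starting on or after the start of study treatment". An upper limit follows, set at 30 days past the final dose or at the point where open-label ribociclib plus fulvestrant begins. The table is by lowest ATC class, preferred term and arm, on the safety set.

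Protocol 10.3 names two groups for the same summaries. The first is drugs started on or after first dose. The second is "medications starting prior to the start of study treatment and continuing after the start of study treatment". Drugs that both began and ended before treatment are only to be listed.

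The primary-analysis SAP, Section 3.7, has both groups as numbered items 1 and 2, followed by "All concomitant therapies will be listed".

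**The concern.** The final-CSR rule keeps the first of the two groups, adds a cut-off for the cross-over, and has nothing in place of the second group. A table built to that rule shows only new starts. Treatment that patients brought into the trial and stayed on does not appear in it.

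The drugs for which this matters are those that may legitimately be ongoing at baseline. Protocol 6.6.2 lets moderate CYP3A4/5 inhibitors and inducers, and drugs with a possible QT risk, be used with caution. A patient can therefore enter on one of them and continue without a protocol deviation. Table 6-6 asks for a review of concomitant medication when QTcF is prolonged, and Table 6-5 names other drugs among the confounders of liver-test rises. A reader who wants to know how common such co-medication was in each arm would look to this table.

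There is also a question of consistency between reports. The primary report counts continuing drugs and the final report would not, so the count for a long-term drug class could fall from one to the other although follow-up is longer.

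**Working it through.** The documents give no figure on this point, so there is nothing to recompute. The check is to run three kinds of drug through each text.

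| Text | Began and ended before first dose | Began before first dose, continued on treatment | Began on treatment |
|---|---|---|---|
| Final-CSR SAP 3.6, definition | Depends on when the assessment period starts, which 3.6 does not say | Concomitant | Concomitant |
| Protocol 10.3 | Listed only | In the summary | In the summary |
| Primary-analysis SAP 3.7 | Flagged in the listing | In the summary (item 2) | In the summary (item 1) |
| Final-CSR SAP 3.6, table rule | Not in the table | **Not in the table** | In the table |

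1. The middle column is where the texts part. Three of the four treat the continuing drug as concomitant. The fourth selects on start date alone and rejects it.
2. The result does not hang on the undefined assessment period. Whether that period opens at consent, at screening or at first dose, a drug begun before first dose and still taken afterwards overlaps it.
3. Missing data do not explain the narrower rule. Protocol 6.6.1 requires medications given within 30 days of study entry and during the study to be recorded on the eCRF, and Protocol 7.1.1.3 requires the same for the 30 days before first dose, with continual updating.
4. Neither Section 3.6 nor any other part of the final-CSR SAP available here announces or explains a departure from Protocol 10.3.

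**The case against.** Several points can be made against reading much into this, and most of them stand.

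- **The listing.** A reader might infer that the all-patient listing has gone too, because the sentence "All concomitant therapies will be listed" was not carried forward. The documents do not support that. Section 3.6 assigns the safety set to all concomitant-medication tables and listings, and says that medications are listed also for the cross-over period. Both phrases presuppose a main listing, and Protocol 10.3 still requires listing by patient.
- **Loss of information.** A reader might infer that the study never reports these drugs. It does. Enrollment closed in June 2016, at most 3 days may separate randomization from Cycle 1 Day 1 (Protocol 7.1), and the primary analysis was in January 2018. Drugs begun before first dose were therefore a closed category by then, and the primary-analysis rule included them.
- **QT and hepatic interpretation.** A reader might infer that known-risk QT drugs or strong CYP3A4/5 agents would drop out of sight. Exclusion criteria 17a and 18 bar patients who cannot stop them, Protocol 6.6.3 prohibits them on treatment, and the final-CSR SAP (3.2) tabulates protocol deviations and lists all of them. Bisphosphonates and denosumab are poor examples as well, since nothing in the documents ties them to QT or liver events. No QT or liver analysis in the final-CSR SAP uses this table.
- **Wording.** The rule says that the summary will include these drugs, not that it will include only these. The sentence may simply have lost a clause when the cross-over cut-off was added, and the table shells, which are not available here, may carry the fuller rule. That is possible, but it is the only inclusion rule the section gives, and a programmer who follows it would leave the continuing drugs out.

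What remains is the conflict in the text and an incomplete table if the text is followed.

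**Conclusion.** The inconsistency is real and minor. As written, the table rule in Section 3.6 of the final-CSR SAP disagrees with that section's own definition and with Protocol 10.3, and it drops the second item of the primary-analysis rule. The consequence is a by-arm table in the final report that omits drugs begun before first dose and continued, caution-list drugs among them, and that cannot be compared with its counterpart in the primary report.

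Its size cannot be stated. It is tempting to suppose that long-term medicines make up much of the co-medication in this population, but the documents give no count and no basis for one.

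The conclusion assumes that the rule is programmed as worded. A rationale in a part of the SAP not available here cannot be excluded, but it would not remove the conflict with Protocol 10.3. No efficacy result, error rate or planned safety comparison depends on this table.

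**What to change.** In Section 3.6 of the final-CSR SAP, add a second category to the summary rule: medications begun before the start of study treatment and continuing after it, as in Protocol 10.3. Item 2 of Section 3.7 in the primary-analysis SAP already supplies the wording. The cross-over cut-off can stay as it is. Check that the table shell and programming specification match.

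If the narrower table was intended, say so, justify the departure from Protocol 10.3, bring the definition into line, and add a footnote that the table is not comparable with the one in the primary report.

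The cost is one clause and the matching selection step in the program. No new data are needed.

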3.7 Safety evaluation

The assessment of safety will be based mainly on the frequency of adverse events and on the number of laboratory/ECG values that fall outside of pre-determined ranges. Other safety data (e.g., vital signs and special tests) will be considered as appropriate.

All safety outputs will use the safety set. The safety summary tables will include ‘double-blinded on-treatment’ events/assessments, i.e., those collected on or after the first date of study treatment and collected no later than 30 days after the date of last study treatment administration or the date of the day prior to the start of cross-over open-label ribociclib plus fulvestrant treatment. The AEs started before the first dose but worsening during the treatment period are also considered as ‘on-treatment’ events.

Key safety analyses that include data from the cross-over on-treatment period will also be performed on the cross-over analysis set. See Section 2.1.8 for more details on the definition of ‘on-treatment’ event during the cross-over on-treatment period.

3.7.1 Adverse events (AEs)

3.7.1.1 Coding of AEs

Adverse events are coded using the Medical Dictionary for Regulatory Activities (MedDRA) terminology.

3.7.1.2 Grading of AEs

AEs will be assessed according to the Common Terminology Criteria for Adverse Events (CTCAE) version 4.03.

The CTCAE represents a comprehensive grading system for reporting the acute and late effects of cancer treatments. CTCAE v4.03 grading is by definition a 5-point scale generally corresponding to mild, moderate, severe, life threatening, and death.

If CTCAE grading does not exist for an adverse event, grades 1 – 4 corresponding to the severity of mild, moderate, severe, and life-threatening will be used. CTCAE grade 5 (death) will not be used in this project; if an AE results in death it will be documented in the outcome (“fatal”). Information on deaths will also be collected on the ‘Death’ CRF.

3.7.1.3 General rules for AE Reporting

AE summaries will include all AEs starting on or after study Day 1 (i.e., on or after the day of the first intake of study treatment) and starting no later than 30 days after the last administration of study treatment or the date of the day prior to the start of cross-over open-label ribociclib plus fulvestrant treatment (see [Section 2.1.5](#)). All AEs will be listed. AEs starting prior to study Day 1 and AEs starting later than 30 days after the last treatment date or the date of the day prior to the start of cross-over open-label ribociclib plus fulvestrant treatment will be flagged in the listings. AEs starting during the cross-over on-treatment period will be listed separately.

AEs will be summarized by presenting the number and percentage of patients having at least one AE, having at least one AE in each primary system organ class, and for each preferred term using MedDRA coding. A subject with multiple occurrences of an AE will be counted only once in the AE category.

Separate AE summaries will be presented by primary system organ class, preferred term, and maximum grade. A patient with multiple grades for an AE will be summarized under the maximum grade recorded for the event. AE with missing CTCAE grade will be included in the ‘All grades’ column of the summary tables.

In AE summaries the primary system organ class will be presented alphabetically and the preferred terms will be sorted within primary SOC in descending frequency. The sort order for the preferred term will be based on their frequency in the ribociclib arm.

The frequency of grade 3 and 4 AEs will be summarized separately.

Any information collected (e.g., grades, relationship to study treatment, action taken etc.) will be summarized and listed as appropriate.

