#### **4.1.2 Treatment phase**

Patient eligibility will be checked once all screening procedures are completed. An eligibility review and confirmation will be embedded to the Interactive Response Technology (IRT) system. Please refer to and comply with detailed guidelines in the IRT manual. The IRT system will confirm the inclusion of eligible patients and randomize them in a 2:1 ratio to one of the two treatment groups described in [Section 4.1](#).

Patients may continue study treatment until disease progression, occurrence of unacceptable toxicity, withdrawal of consent by the patient, patient is lost to follow-up, or the sponsor terminates the study. Patients will be followed for survival regardless of treatment discontinuation for any reason, and regardless of achieving the primary endpoint, until the planned number deaths for final OS analysis have been documented (except if consent is withdrawn or patient is lost to follow-up). An end of treatment visit will be performed when patients permanently discontinue study treatment.

All patients will have PK sampling; a subset (of approximately 150 patients) will have sparse PK collections on 3 occasions while the remainder will have a single trough PK sample on 3 occasions as detailed in [Section 7.2.3](#).

Following protocol amendment 4, study participants will be unblinded, with an opportunity for those patients still in the study in the arm of placebo + fulvestrant to transition to the treatment of ribociclib + fulvestrant.

Crossover is optional and will be conducted only upon documented consent of the study patient and protocol amendment 4 approval. A list of procedures to be performed is summarized in [Table 7-1b](#).

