1.2 Objectives

The study objectives and corresponding endpoints as specified in the protocol are provided in [Table 1-1](#). PFS, as assessed by the local radiologists/investigators and using RECIST 1.1 criteria is the primary endpoint. Overall survival is a secondary endpoint. Both PFS and OS have been tested statistically significant and results have been summarized by previous study reports.

Table 1-1 Study objectives

Objective	Endpoint
Primary	
To compare PFS between ribociclib in combination with fulvestrant to placebo in combination with fulvestrant among men and postmenopausal women with HR+, HER2-negative advanced breast cancer who received no or only one prior endocrine treatment for advanced disease	PFS based on local radiology assessments and using RECIST 1.1 criteria
Secondary	
To compare the two treatment arms with respect to overall survival.	Overall survival
To evaluate the two treatment arms with respect to overall response rate, clinical benefit rate, time to response and duration of response.	ORR as defined by RECIST 1.1. CBR, defined as percentage of patients with CR, PR or SD lasting 24 weeks or longer, TTR, DOR per RECIST 1.1
To evaluate the two treatment arms with respect to time to deterioration of ECOG performance status.	Time to definitive deterioration of ECOG performance status from baseline
To evaluate the safety and tolerability of ribociclib in combination with fulvestrant.	Frequency/severity of AEs, laboratory abnormalities
To evaluate patient reported outcomes for health-related quality of life in the two treatment arms.	Time to 10% deterioration in the global health status/QOL scale score of the EORTC QLQ-C30 Change from baseline in the global health status/QOL scale score of the EORTC QLQ-C30
To characterize the pharmacokinetics (PK) of ribociclib (and relevant metabolites such as LEQ803) when given in combination with fulvestrant.	Concentration by time point for ribociclib (and relevant metabolites such as LEQ803)

Objective	Endpoint

2 Definitions and general methodology

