2.1.8 On-treatment assessment/event

Safety summaries and selected summaries of deaths will summarize only on-treatment assessments/events.

Double-blind on-treatment period:

An on-treatment assessment/event is defined as any assessment/event in the following time interval:

[date of first administration of study treatment, the earliest between the date of last administration of study treatment + 30 days and the date of first administration of cross-over open-label ribociclib plus fulvestrant treatment – 1 day], i.e., including the lower and upper limits.

The double-blind on-treatment period is the **default** on-treatment period used in the analyses unless specified otherwise.

Cross-over on-treatment period:

An on-treatment assessment/event is defined as any assessment/event in the following time interval: [date of first administration of the cross-over open-label ribociclib plus fulvestrant treatment, date of last administration of the cross-over open-label ribociclib plus fulvestrant treatment + 30 days], i.e., including the lower and upper limits.

(Note: However, the calculation of study treatment duration will use different rules as specified in [Section 3.5.1](#)).

An AE started in the screening phase and ongoing in the on-treatment phase will not be considered as an on-treatment AE unless it has worsened.

If the last date of study treatment is missing, any assessment/event occurring after the start of study treatment will be considered as on-treatment.

Data listings will include all assessments/events, flagging those which are not on-treatment.

Note: The date of first administration of study treatment and the date of last administration of study treatment are defined in [Sections 2.1.4](#) and [2.1.5](#), respectively.

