3.7.1.5 Grouping of adverse events of special interest

An adverse event of special interest is a grouping of adverse events that are of scientific and medical concern specific to ribociclib. These groupings are defined using MedDRA terms, SMQs (standardized MedDRA queries), HLGs (high level group terms), HLTs (high level terms) and PTs (preferred terms). Customized SMQs (Novartis MedDRA queries, NMQ) may also be used. A NMQ is a customized group of search terms which defines a medical concept for which there is no official SMQ available or the available SMQ does not completely fit the need. It may include a combination of single terms and/or an existing SMQ, narrow or broad. For each specified AESI, the number and percentage of patients with at least one event of the AESI occurring during the double-blinded on-treatment period will be summarized.

Summaries of these AESIs will be provided by treatment arm, (specifying grade, SAE, relationship, leading to treatment discontinuation, leading to dose adjustment/interruption, etc.).

A Case Retrieval Sheet (CRS) with the exact composition of the AE groupings is to be used to map reported AEs to the AESI groupings. This file may be updated (i.e., it is a living document) based on review of accumulating trial data, and therefore the groupings are also subject to potential change. The most up-to-date version of the CRS will be used at the time of the analysis.

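### The final-report SAP gives adverse events by arm only as crude percentages, over a window expected to be longer on ribociclib, and drops the time-to-first-event analyses planned earlier

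*SAP*

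**What the plan says.** The SAP file holds two plans: one for the final study report (based on protocol amendment 4) and one for the primary PFS analysis (based on amendment 2).

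In the final-report SAP:
- Section 3.7.1.3 states that "AEs will be summarized by presenting the number and percentage of patients having at least one AE", and that "A subject with multiple occurrences of an AE will be counted only once in the AE category". The tables listed in 3.7.1.4 (all events, grade 3-4, serious) apply that rule by arm.
- Section 3.7.1.5 does the same for events of special interest: "the number and percentage of patients with at least one event of the AESI occurring during the double-blinded on-treatment period will be summarized".
- Section 2.1.8 sets the default window. It opens at first dose and closes at "the earliest between the date of last administration of study treatment + 30 days and the date of first administration of cross-over open-label" treatment, less one day. The last dose is that of any component (2.1.5).
- Section 3.5.1 tabulates duration of exposure by arm but does not link it to event frequency. Section 4 covers only duration of follow-up. No patient-year rate, fixed-time cumulative incidence or time-to-first-event estimate for adverse events appears.
- Section 1.2 records that "Both PFS and OS have been tested statistically significant and results have been summarized by previous study reports".

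The Protocol (4.1.2) sets treatment duration: "Patients may continue study treatment until disease progression, occurrence of unacceptable toxicity, withdrawal of consent by the patient", among other reasons.

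The primary-analysis SAP planned more. Its 3.9.2 has Kaplan-Meier time to first grade 2 or worse, and grade 3 or worse, neutrophil and ALT/AST toxicity, and failure curves by arm for time to first adverse event. Its 3.9.4 has time to grade 2 or worse QTcF prolongation.

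**The concern.** A crude percentage depends on how often an event occurs per unit of time and on how long patients are watched. Here the watching time is tied to the efficacy outcome. If ribociclib delays progression, its patients stay in the window longer and have more time to record a first event of any kind. Placebo windows can also be closed by cross-over, which ribociclib windows cannot.

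Safety and tolerability is a secondary objective and makes up most of the comparative content of the final report. With percentages alone, a reader cannot tell an excess event rate from longer observation. The exposure table shows that an imbalance exists but does not allow correction of any given event term.

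**Working it through.** **Inputs.** Control median PFS 9 months, ribociclib median 13.4 months and hazard ratio 0.67 (primary-analysis SAP 3.16; Protocol 10.8). The 30-day tail is from final-report SAP 2.1.8. The documents give no event rates and no observed exposure, so the following are assumptions: PFS medians stand in for time on treatment, exposure is exponential, follow-up is capped at 60 months, and the event hazard is constant and equal in both arms.

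**The plan's own figure.** 9 / 0.67 = 13.43 months, against the stated 13.4. It reproduces.

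**Crude percentage.** With event hazard λ, discontinuation rate μ = ln 2 / median, cap C = 60 months and tail w = 30 / 30.4375 = 0.986 months:

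P = 1 − e^(−λw) × [ μ/(μ+λ) × (1 − e^(−(μ+λ)C)) + e^(−(μ+λ)C) ]

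At λ = 0.02 per month, e^(−λw) = 0.9805.
- Placebo: μ = 0.0770; bracket = 0.7938 × 0.9970 + 0.0030 = 0.7944; P = 1 − 0.9805 × 0.7944 = 22.1%.
- Ribociclib: μ = 0.0516; bracket = 0.7207 × 0.9864 + 0.0136 = 0.7245; P = 1 − 0.9805 × 0.7245 = 29.0%.

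That is 6.9 points and a ratio of 1.31 with no true difference. The mean windows are 13.8 and 19.5 months, a ratio of 1.41.

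**Other event rates (equal in both arms).**

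| Hazard per month | Per 100 patient-years | Placebo % | Ribociclib % | Difference (points) | Ratio |
|---|---|---|---|---|---|
| 0.005 | 6 | 6.5 | 9.0 | 2.5 | 1.38 |
| 0.01 | 12 | 12.3 | 16.7 | 4.4 | 1.35 |
| 0.02 | 24 | 22.1 | 29.0 | 6.9 | 1.31 |
| 0.05 | 60 | 42.3 | 51.5 | 9.3 | 1.22 |
| 0.1 | 120 | 60.6 | 69.2 | 8.6 | 1.14 |
| 0.3 | 360 | 84.8 | 89.1 | 4.3 | 1.05 |

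The ratio is worst for low-rate events; the absolute gap is widest at middle frequencies.

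**Sensitivity at 0.02 per month.**
- Exposure hazard ratio 0.8: 22.1% vs 25.8%, ratio 1.17. Exposure hazard ratio 0.5: 22.1% vs 34.5%, ratio 1.56.
- 36-month cap: 21.5% vs 27.3%, ratio 1.26. No cap: 22.2% vs 29.3%, ratio 1.32.
- The plan's 40/60 first-line/second-line mix (control medians 18 and 6.5 months), 60-month cap: 24.2% vs 30.8%, ratio 1.27.

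**Time-aware measures on the same case.** Cumulative incidence at 12 months is 1 − e^(−0.02×12) = 21.3% in both arms. The patient-year rate is 1200 × 0.2210 / 11.05 = 24.0 on placebo and 1200 × 0.2897 / 14.48 = 24.0 on ribociclib, where 11.05 and 14.48 are the mean months to first event or end of window.

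**Early-onset events.** Take a hazard of 0.1 per month in both arms, confined to the first two months.
- Crude: 17.8% placebo, 17.9% ribociclib, ratio 1.01. There is almost no distortion.
- Patient-year rate: 1200 × 0.1780 / 11.51 = 18.6 on placebo and 1200 × 0.1791 / 16.13 = 13.3 on ribociclib, ratio 0.72.
- With a true 1.4-fold early hazard on ribociclib, the crude ratio is 24.1 / 17.8 = 1.36, but the patient-year ratio is 19.4 / 18.6 = 1.04.

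**The case against.** The strongest reply is that the obvious remedy can do more harm than the defect. If patient-year rates became the basis for comparing arms, the last calculation shows that they would make ribociclib look 28% safer for an early event with no true difference, and would nearly hide a real 1.4-fold excess. Protocol 1.2.1.2.1 describes this pattern for the drug's known toxicities: neutropenia typically by Day 15, and QT changes visible in the first cycle by Day 8. Crude percentages err towards blaming the drug; patient-year rates can err towards clearing it. This stands, and it determines the fix.

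Three further points also stand in part. The final-report SAP is descriptive: it specifies no between-arm test, difference or ratio for adverse events, and it follows the protocol endpoint of frequency and severity. Time-aware safety analyses were already planned for the primary report, so the gap lies in not carrying them forward. And closing the placebo window at cross-over is not an error in itself, because it keeps events on ribociclib from being counted under placebo.

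A reader might also infer that ribociclib exposure is known to be longer, or that the reported excess of events is an artefact. The documents support neither. They contain no observed exposure by arm, and discontinuation for toxicity would narrow the gap, although patients who stop ribociclib may stay on fulvestrant (Protocol 6.1.2) and so remain in the window.

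**Conclusion.** The point holds as a gap in the final-report SAP: it has no adverse-event measure that separates event rate from time observed, and it omits the time-to-first-event analyses of the primary-analysis SAP. Under the planning assumptions, an event occurring at 24 per 100 patient-years in both arms would appear as about 22% vs 29%, with a ratio between 1.17 and 1.56 across the exposure hazard ratios tried. The longer ribociclib window is inferred from treatment to progression, the significant PFS result and the cross-over cut.

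The distortion is not uniform. It matters most in relative terms for low-rate events that accrue over the whole treatment period, and hardly at all for events in the first two months or for near-universal ones. It would therefore be wrong to conclude that the crude tables mislead throughout, or that patient-year rates should replace them.

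**What to change.** In final-report SAP 3.7.1.3 to 3.7.1.5:
- Keep the crude tables as planned.
- Carry forward time-to-first-event (cumulative incidence) estimates by arm with 95% confidence intervals, including at fixed times such as 12 months, for events of special interest, serious events and grade 3-4 events. State how death and the end of the window are handled.
- Add, as a supplementary table, exposure-adjusted incidence per 100 patient-years, counting first events over time to the event or the end of the window. Note that it must not be used alone for early-onset events such as neutropenia and QTcF prolongation.

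The cost is a few more tables built from dates already derived (first dose, event onset, end of window). The main drawback is that patient-year rates assume a constant hazard, which is why they are supplementary.
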